6.3 Study procedures

6.3.1 Screening procedures

Patients are recruited from a specialised centre for bipolar disorders in psychiatric hospital (Centrum Bipolair GGzE). The responsible lead clinician (regie behandelaar) identifies eligible patients and subsequently give these patients the information letter as well as oral information about the study and asks permission to hand over their contact information to the researcher should they consider participating. Once patients have indicated to the researcher, their nurse, psychiatrist or psychologist they would like to participate in this study, the researcher makes an appointment with the patient. During this appointment the researcher checks if the identified patient meets the inclusion criteria, and if patients still agrees with participation in the study and they are given the informed consent letter. After one week in which patients can consider their participation in this study, the researcher makes another appointment with the participant during which both the researcher and

participant sign the informed consent letter. At this time, the researcher asks for the email address of the participants in order for the online questionnaires to be accessible for the patient.

6.3.2 Study Assessment Moments

Psychoeducation groups at Centrum Bipolar start once in every six weeks. At four weeks prior to the start of each psychoeducation group the identified participants start with the online measures at baseline (T0), and both daily and weekly online measurements which participants receive by email. Note here that the patients that participate in this study will not wait longer than the patients that choose not to participate. Participants continue to fill in both the daily and weekly online measures for four weeks (the baseline period). After four weeks all participants fill in the measures pre-intervention (T1), and are allocated randomly to either the ImCT or psychoeducation condition, which will then commence. During the intervention period (12 weeks for the ImCT condition, and 6 weeks for the psychoeducation treatment condition) all participants continue to fill in both the daily and weekly online measures. At the end of the intervention, all participants fill in the post-intervention measures (T2) online. Subsequently, all participants continue to fill in both daily and weekly online measures until the end of the study (at follow up at 16 weeks). In addition, participants fill in the post-intervention online measures at follow up at 8 weeks (T3) and 16 weeks (T4) after the end of intervention.

6.3.3 Assessment Procedures

All measures are administered online. However, there is an option to fill in the questionnaires on paper, should this prove difficult for participants. The daily measures will take a 2 to 3 minutes, the weekly measures will take approximately 20 minutes. The measures at baseline (T0), pre-intervention (T1), post-intervention (T2) and at 8 and 16-weeks follow-up (T3 and T4) will take approximately 45 minutes. Patients and therapist will not be informed about the results of assessments until the end of the study (16 weeks after the end of intervention).

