4.3 Exclusion criteria

A potential subject who meets any of the following criteria will be excluded from participation in this study:

- Learning difficulties, organic brain disease or severe neurological impairment.
- Have received either 1) psychoeducation similar to the presently used psychoeducation program, or 2) CBT tailored at bipolar disorder with or without imagery interventions within the last year prior to the start of the study.
- Current severe substance or alcohol misuse (clinicians assessment).

- Current manic episode as diagnosed by DSM-5
- Current active psychotic symptoms
- Presence of active suicidal risk as indicated by a score of 2 or more on item 12 (i.e. frequent thought and/or plans to end their life) of the QIDS (Rush et al., 2003) confirmed by convergent clinical opinion.
- Taking part in concurrent treatment studies investigating pharmacological or psychological treatment for BD.

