5. TREATMENT OF SUBJECTS

5.1 Investigational product/treatment

Both ImCT and psychoeducation interventions are preceded by a period of 4 weeks baseline, in which they start to monitor their mood both daily and weekly, start or continue sessions with a psychiatrist (see below). Both groups will either start or continue to have regular sessions with their psychiatrist throughout the study, aimed at advice on pharmacotherapy, monitoring and if necessary adjustment of pharmacotherapy.

Description of ImCT:

The participants receive ImCT for a period of 12 weeks, 12 sessions of 60 minutes. This intervention consists of an in-depth identification (4 sessions) of images followed by imagery interventions, (6 sessions) and a consolidation phase (2 sessions) developed by Holmes, Young, Hales and DiSimplico and described in the ImCT manual (in press). The in-depth

identification consists of identifying problematic imagery, constructing a micro-formulation with the participant along the lines of regular CBT. In this micro-formulation, first triggers of problematic imagery are identified, then both quality and appraisals of this image are identified. Subsequent maladaptive behaviour and possible links with earlier experiences are described, as well as other maintaining factors. The imagery intervention consists of metacognitive imagery intervention, rescripting of imagery, promoting positive imagery or competing imagery tasks (or a combination of these). In addition, relapse prevention strategies are practiced before the end of this intervention. To increase treatment integrity, therapist in the ImCT condition receive weekly supervision from the Imagery Research group (from Oxford, London and Stockholm) via skype. Therapists are qualified psychologist carefully trained in ImCT.

Detailed description of psychoeducation:

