The psycho-education lasts for a period of 6 weeks, consisting of 6 2-hour sessions. Psycho-education is offered in groups, using the format described in by Postma and colleagues (Postma, Honig, & van Gent, 2008). In the first three sessions patients are receiving information on bipolar disorder, symptoms, prevalence, aetiology and mood stabilisers. The remaining sessions focus on (early) recognition of mood variations, and management or coping strategies. Finally, medication adherence strategies and relapse strategies are discussed. Nursing staff who run the psychoeducation groups are experienced in running these groups and carefully trained in the psychoeducation method according to guidelines from Trimbos.

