5.2 Use of co-intervention (if applicable)

Both groups (ImCT and psychoeducation) maintain their regular consults with a psychiatrist or specialised nurse practitioner and receive advice and guidance on medication, which is monitored and adjusted conform guidelines (Goodwin et al., 2016; Kupka et al., 2015) throughout this study. These guidelines recommend using a mood stabiliser, with specific recommendation for additions in episodes of mania and depression. Where possible the above-mentioned guidelines will be adhered to unless individual circumstances warrant deviations from this. Consultation with the psychiatrist or specialised nurse practitioner will start (or continue should patients already be in care) during the baseline period, intervention period and follow-up period.

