6. METHODS

6.1 Study parameters/endpoints

6.1.1 Main study parameter/endpoint

To assess the primary endpoint of this study (1), decrease of mood variability, mood variability is measured using the Affect Lability Score Short Version (ALS-18) (Oliver & Simons, 2004) at baseline (T0), pre- intervention (T1) and post intervention (T2), and at follow-up measurements at 8 (T3) and 16 weeks (T4) after treatment discontinuation in both the ImCT and psychoeducation conditions. The ALS-18 is a self-report scale measuring lability in affect and consists of 18 items. Ratings are made on a 4-point scale with a maximum score of 72. Scores range from A= very characteristic of me (4 points), to D= very uncharacteristic of me (1 point).

In addition we monitor changes in mood variability using the National Institute of Mental Health Life Chart Methodology (NIMH-LCM) Prospective Self-Rating (Denicoff et al., 2000). Participants rate their mood (both mania and depression) on a 9-point Likert scale, ranging from -4 (severe depression, admission required due to severe dysfunction) to 0 (stable mood) to +4 (severe mania, admission required due to severe dysfunction). Daily measurements are calculated during a 4-week baseline prior to start of either ImCT or psychoeducation, during the intervention and until follow up at 16 weeks. This method is advised given that traditional self-report mood ratings over a single time point are scarcely representative of mood variability in bipolar disorder.

6.1.2 Secondary study parameters/endpoints (if applicable):

The following parameters are used for the following secondary objectives:

To assess (2a) level of depression, mania and anxiety and (2b) general functioning and hopelessness (3) number of relapses into mania or depression decline/increase, we administer the following measures:

- Level of depression, using the Quick Inventory of Depressive Symptoms (QIDS-SR) (Rush et al., 2003). The QIDS-SR is a 16-item self-report rating scale in which the nine DSM 5 symptoms of major depression are incorporated. Answers are rated on a four-point Likert scale (0-3). The QIDS-SR is administered weekly throughout the duration of the study.

- Level of mania, using the Altman Self-Rating Mania Scale (ASRM-NL) (Altman, Hedekker, & Peterson, 1997). The ASRM-NL is a 5 item self-report instrument to measure severity of mania symptoms. This is administered weekly throughout the duration of the study.

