6.2 Randomisation, blinding and treatment allocation

An independent central research assistant will randomize participants to treatment condition (ImCT or psychoeducation) after checking all in- and exclusion criteria. Randomization will be based on block randomization with (N=10) per block to guarantee a balance between conditions over time and stratified for mood stabilising medication (either mood stabilising medication, or no mood stabilising medication), so that mood stabilising medication is controlled per arm. Stratification for mood stabilising medication is necessary because not using mood stabilizing medication can seriously affect the primary outcome variable. We roughly estimate that 15 percent of the participants in GGzE will have no mood stabilising medication, but there are no firm data available. Blinding of participants and therapists to treatment condition is not possible in this kind of psychotherapy trial, but the assessments will be blind to treatment condition as they are filled in online.

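### After randomisation no one is required to read or act on item 12 (suicidality) of the weekly QIDS-SR, and the withholding rule in section 6.3.3 has no safety exception

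*Combined protocol and SAP*

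**What the plan says.** **Entry.** Section 4.3 lists as an exclusion: "Presence of active suicidal risk as indicated by a score of 2 or more on item 12" of the QIDS, "confirmed by convergent clinical opinion". It explains such a score as frequent suicidal thoughts or plans. It does not say which form of the QIDS is used. Section 6.2 has participants randomised "after checking all in- and exclusion criteria", and section 6.3.2 places randomisation at the end of the four-week baseline.

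**After entry.** Section 6.1.2 states: "The QIDS-SR is administered weekly throughout the duration of the study". Under 6.3.2 and 6.3.3 the weekly forms are self-completed online, with a paper option, until 16 weeks after the intervention. Their stated uses are the depression outcome and a relapse count from a QIDS cut-off of 10 (sections 6.1.2 and 8). Item 12 is not mentioned again.

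**Withholding.** Section 6.3.3: "Patients and therapist will not be informed about the results of assessments until the end of the study", which it defines as 16 weeks after the intervention. Under section 10.1 only the lead researcher can link participant numbers to names.

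**Clinical contact.** For ImCT: "The participants receive ImCT for a period of 12 weeks, 12 sessions of 60 minutes". For the comparator: "The psycho-education lasts for a period of 6 weeks, consisting of 6 2-hour sessions". Under section 5.2 both arms "maintain their regular consults with a psychiatrist or specialised nurse practitioner" through baseline, treatment and follow-up.

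**The concern.** The protocol sets its own marker of possible active suicidal risk, uses it to keep patients out, and then asks for the same information every week for 26 to 32 weeks without saying who looks at it. If the written procedure is followed exactly, a score of 2 or more after randomisation can stay unread until the patient has finished the study. A clinician may still learn of the risk at a session or consult, but only if the patient raises it or staff notice it.

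Patient safety is at stake. Section 1 describes suicide risk in this disorder as high. Section 4.3 excludes a current manic episode but not a current depressive one. Sections 7.4 and 10.2 dispense with a DSMB and a monitoring plan, so no other body is assigned to look at these data.

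**Working it through.** The protocol gives no figure to reproduce on this point. The check has two parts: a search for any duty to review item 12, and a count of the forms involved.

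**1. Is any safeguard linked to the score?**

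| Provision | Section | Tied to item 12 after randomisation? |
|---|---|---|
| Eligibility check | 6.2 | No. It ends at randomisation, and review of the weekly baseline scores is not specified |
| Psychiatrist or nurse practitioner consults | 5.2 | No. Frequency not stated |
| Treatment sessions | 5.1 | No. The therapist is not told the results |
| Usual care on relapse | Summary, 11.1 | No |
| Withdrawal for urgent medical reasons | 6.4 | No. At the investigator's discretion |
| Exclusion after a relapse admission of over one week | 6.4.1 | No |
| Termination if many ImCT patients drop out or deteriorate | 6.7 | No |
| Suspension for subject safety | 7.1 | No |
| AE and SAE recording | 7.2 | No. AEs come from spontaneous report or staff observation |

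None names a reader, threshold, alert, time limit or action for the item.

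**2. How many forms?**

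Inputs: 48 patients per arm (section 4.4); study duration 32 weeks for ImCT and 26 for psychoeducation, including 4 weeks of baseline (section 3); treatment of 12 and 6 weeks (section 5.1); follow-up of 16 weeks (section 6.3.2). Assumption: one form per week, all completed, no dropout. The counts are therefore maxima.

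- Weeks after randomisation: ImCT 32 − 4 = 28; psychoeducation 26 − 4 = 22.
- Forms after randomisation: 48 × 28 = 1,344 and 48 × 22 = 1,056; total 2,400.
- Forms in weeks with a scheduled session: 48 × 12 + 48 × 6 = 576 + 288 = 864, and 864 / 2,400 = 36%.
- Forms in follow-up: 96 × 16 = 1,536, and 1,536 / 2,400 = 64%.
- Ratio of forms per patient between arms: 28 / 22 = 1.27, so 27% more in ImCT.
- Flags for each 1% of post-randomisation forms at 2 or more: 2,400 × 0.01 = 24. These are forms, not patients, since one patient can score 2 or more repeatedly.

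The documents give no rate of item 12 at 2 or more, so the number of patients affected cannot be calculated.

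**The case against.** The strongest reply is that 6.3.3 does not cause the gap. It withholds results from patients and the therapist only. A reader might infer that it forbids any safety response, but the text does not support that: the lead researcher, psychiatrist and nurse practitioner are free to look. This stands, and it means that deleting the sentence would not solve the problem. What is missing is a duty, and permission to look does not supply one.

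Second, patients remain in care at a specialised bipolar centre, with consults in every phase, and those at active risk are excluded at the start. This also stands. A reader who concludes that patients are left without clinical cover goes beyond the documents. The gap concerns a signal that the trial itself collects.

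Third, an alert procedure could exist in the consent material, which is not in the review copy, or in a local crisis procedure. That cannot be ruled out. However, the sections on assessment, withdrawal and safety are all present, and a provision of this kind should appear or be cited there.

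Fourth, form counts do not measure risk. That is correct. It would be tempting to add the baseline forms and report the share of all weeks without a treatment session as weeks without contact. The documents do not support that figure: baseline precedes the eligibility check, and the frequency of consults is not stated.

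**Conclusion.** The point holds in a limited form. After the check at randomisation, the protocol requires no one to read or act on item 12 of the weekly QIDS-SR, although section 4.3 treats a score of 2 or more, once clinically confirmed, as active suicidal risk. Section 6.3.3 adds a withholding rule with no safety exception. The general safeguards reduce the risk but do not depend on the score.

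Up to 2,400 forms are involved, 1,536 of them after treatment sessions have ended. This assumes 48 patients per arm and full completion. It describes how much information goes without a required reader. It does not show how many patients are at risk, and no claim about harm can be built on it.

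The change should be made because it improves patient safety at small cost. Confidence is medium, since a provision outside the review copy may exist.

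**What to change.** Add to the end of section 6.3.3:

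> Exception: a score of 2 or more on item 12 of any weekly QIDS-SR, including the baseline weeks, is flagged to the lead researcher, who promptly (within a time limit the sponsor sets) passes it to the treating psychiatrist or specialised nurse practitioner for clinical assessment under usual care. All other scores stay withheld. The rule is the same in both arms, and flags are reported by arm.

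Add one sentence on this to the information letter. If a local procedure already provides it, cite that procedure in 6.3.3 instead. The time limit, and any cover for the lead researcher's absence, are for the sponsor to decide.

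**Cost and downsides**
- An amendment notified to the METC and, if substantial, to the competent authority (section 10.3).
- Checking time for existing staff. The protocol does not say whether Research Manager can send an alert.
- One clinical contact per flag: about 24 for each 1% of post-randomisation forms, plus any flags in baseline.
- About 27% more opportunities for a flag per patient in ImCT than in psychoeducation, so extra contacts may be unequal in an unblinded trial. Reporting flags by arm makes this visible.
- Patients who know of the rule may answer item 12 differently. It is one of 16 items in a secondary outcome that also defines depressive relapse.

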6.4 Withdrawal of individual subjects

Subjects can leave the study at any time for any reason if they wish to do so without any consequences. The investigator can decide to withdraw a subject from the study for urgent medical reasons.

6.4.1 Specific criteria for withdrawal (if applicable)

If patients experience relapse (mania or depression) and require a hospital admission for longer than one week, they will be excluded from this trial.

6.5 Replacement of individual subjects after withdrawal

Should patients withdraw from the study they will not be replaced.

6.6 Follow-up of subjects withdrawn from treatment

If patients are withdrawn from the study, they will continue with care as usual from the specialised centre for bipolar disorders of the GGzE.

6.7 Premature termination of the study

The study will be terminated if a large number of patients in ImCT condition drop-out or deteriorate. This, however, is not expected as the treatment has been piloted before and found highly effective and to have low drop-out rate.

7. SAFETY REPORTING

7.1 Temporary halt for reasons of subject safety

In accordance to section 10, subsection 4, of the WMO, the sponsor will suspend the study if there is sufficient ground that continuation of the study will jeopardise subject health or safety. The sponsor will notify the accredited METC without undue delay of a temporary halt including the reason for such an action. The study will be suspended pending a further positive decision by the accredited METC. The investigator will take care that all subjects are kept informed.

7.2 AEs, SAEs and SUSARs

7.2.1 Adverse events (AEs)

Adverse events are defined as any undesirable experience occurring to a subject during the study, whether or not considered related to the trial procedure or the experimental intervention. All adverse events reported spontaneously by the subject or observed by the investigator or his staff will be recorded.

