3. STUDY DESIGN

The present research proposal concerns a randomised feasibility trial, comparing ImCT intervention to psychoeducation. In addition to the between group design, the study also uses a within-group design, where ImCT and psychoeducation is preceded by a four-week baseline condition. Note that during this baseline period and throughout the study, all patients will maintain their regular appointments with their psychiatrist or specialised nurse practitioner, who will prescribe, monitor and adjust mood stabilising medication conform guidelines. The within-group design allows participants baselines to act as their individual control periods with no intervention (Barlow, Nock, & Hersen, 2009; Bonsall, Wallace-Hadrill, Geddes, Goodwin, & Holmes, 2012; Holmes et al., 2016). The study will take place within a specialised centre for bipolar disorders within a large psychiatric hospital (GGzE). All participants start after 4 weeks of baseline with either ImCT or psychoeducation treatment. The duration of the study for participants will be 32 weeks for participants in the ImCT condition and 26 weeks for participants in the psycho-education condition. The difference in duration between the conditions is due to treatment length, that is, 12 weeks weekly 1-hour sessions for ImCT and 6 weeks weekly 2-hour sessions for the psychoeducation treatment. Note that all participants will have had 12 hours face-to-face contact in both conditions.

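### Passive adverse-event recording, with unequal reporting occasions and observation windows, can bias any comparison of harms between the arms

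*Combined protocol and SAP*

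**What the plan says.** The collection rule is in section 7.2.1: "All adverse events reported spontaneously by the subject or observed by the investigator or his staff will be recorded". The same section defines an adverse event very broadly, as any undesirable experience during the study. No checklist, scheduled question or adverse-event visit is described anywhere.

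Section 3 gives the treatment schedule as "12 weeks weekly 1-hour sessions for ImCT and 6 weeks weekly 2-hour sessions for the psychoeducation treatment" and adds: "Note that all participants will have had 12 hours face-to-face contact in both conditions". On the control arm, section 5.1 states: "Psycho-education is offered in groups". It describes ImCT as built on a formulation made with the participant. Section 3 also gives the time in study: "The duration of the study for participants will be 32 weeks for participants in the ImCT condition and 26 weeks for participants"; the second figure is for the control arm.

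Some contact is common to both arms. Under section 5.2, "Both groups (ImCT and psychoeducation) maintain their regular consults with a psychiatrist or specialised nurse practitioner", at an interval that is not stated. Under section 6.3.2, "all participants continue to fill in both daily and weekly online measures until the end of the study". Section 6.3.3 limits what is done with the answers: "Patients and therapist will not be informed about the results of assessments until the end of the study". Section 6.2 says that participants and therapists cannot be blinded.

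**The concern.** Under a passive rule, an event is recorded only if the patient raises it or someone on the staff notices it, so the record depends on how often and in what setting that can happen. Here both differ by arm. ImCT offers twice as many sessions, and its content draws out distressing material. Psychoeducation sessions take place in front of other patients, where private events may be harder to raise; that is a reasonable inference, not something the documents state. After treatment neither arm has a scheduled study session for 16 weeks, and T2 to T4 are completed online (with a paper option).

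If true harm were equal, the arms could still show different counts. ImCT could look worse than it is, and late events could be missed in both arms. Little else stands behind the record: section 7.4 dispenses with a DSMB, section 10.2 dispenses with a monitoring plan, and section 6.7 would end the study for drop-out or deterioration in the ImCT arm without giving a threshold or a comparator.

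**Working it through.** **Plan's own figures.** Contact: 12 × 1 h = 12 h and 6 × 2 h = 12 h. Duration: 4 + 12 + 16 = 32 weeks and 4 + 6 + 16 = 26 weeks. Both agree with section 3. The plan gives no adverse-event rate or count, so there is no stated harm figure to reproduce.

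**Window after randomisation.** Without the 4-week baseline, ImCT has 12 + 16 = 28 weeks and psychoeducation has 6 + 16 = 22 weeks. With equal true weekly rates and equal detection, the raw count ratio is 28/22 = 1.27 and the person-week ratio is 1.00.

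**Adding unequal occasions.** Assume that an event is recorded with probability p in a week with a study session and q in any other week, with the same p and q in both arms. The values used are p = 0.3, 0.5, 0.8 and q = 0.1, 0.3, 0.5, with p ≥ q. They are assumptions. Session and other weeks are:

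| Window | ImCT session / other | Psychoeducation session / other |
|---|---|---|
| Full, after randomisation | 12 / 16 | 6 / 16 |
| Common first 22 weeks | 12 / 10 | 6 / 16 |

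- Raw count ratio, full window: (12p + 16q)/(6p + 16q). With p = q it is 1.27. With p = 0.8 and q = 0.1 it is 11.2/6.4 = 1.75.
- Person-week ratio: [(12p + 16q)/28] ÷ [(6p + 16q)/22]. With p = q it is 1.00. With p = 0.8 and q = 0.1 it is 0.400/0.2909 = 1.375, or about 1.37.
- Common 22 weeks: (12p + 10q)/(6p + 16q). With p = q it is 22/22 = 1.00. With p = 0.8 and q = 0.1 it is 10.6/6.4 = 1.66.

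Neither a person-week denominator nor a common window removes the problem by itself. Both correct for time observed but leave unequal detection in place. Within the common 22 weeks ImCT still has 12 session weeks against 6.

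**What the model leaves out.** It uses one p for both arms. Reticence in a group would lower p for psychoeducation and raise the ratios; its longer sessions could raise p and lower them. Unblinded reporting could act in either direction. The ranges are illustrations, not bounds.

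**What the scales already cover.** Relapse is scored in both arms from the weekly ASRM and QIDS-SR during follow-up (section 6.1.2). QIDS item 12 covers suicidal thoughts or plans (section 4.3). The daily NIMH-LCM rates severity up to a level at which admission would be needed (section 6.1.1). None of these is described as recording that an admission, an act of self-harm or a crisis contact took place, and no rule turns an answer into an adverse-event record.

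**The case against.** The strongest reply is that the design is more even than a count of sessions suggests. Contact hours are equal. Sessions are weekly in both arms during treatment, so weeks 1 to 6 after randomisation match and only weeks 7 to 12 differ. Consultations and questionnaires are common to both arms, as is the absence of study sessions in follow-up. The most likely forms of deterioration are measured actively and symmetrically. Section 6.4.1 excludes patients admitted for more than a week because of relapse, so the study must learn of those admissions somehow. Section 8 plans no adverse-event comparison. All of this stands, and it limits the point to a risk of bias.

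A reader might go further and infer that event counts will track contact rather than harm, or that the 12:6 session ratio implies a twofold distortion. The documents do not support either. The 2:1 figure mixes exposure with ascertainment: twice as many treatment weeks would give about twice as many treatment-phase events even with perfect recording.

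A reader might also infer that the planned 350-patient RCT will take its tolerability figures from this record. Section 4.4 says that the trial is to inform that RCT, and section 1 names retention, general feasibility and first comparative data. Neither mentions use of the adverse-event record.

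A last objection is that self-harm items on a form whose results are withheld until study end raise a question of who reviews the answers. That is fair, but the weekly QIDS-SR already raises it. It is a matter for the amendment to settle and does not defeat the change.

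**Conclusion.** The point holds as a risk of differential ascertainment. The passive rule, the 12 individually tailored versus 6 group sessions, the 28- versus 22-week windows and the unblinded reporters are all documented, and no structured enquiry offsets them. The window effect, 1.27 on raw counts, follows from the plan's own figures if true weekly rates and detection are equal. The remaining effect, 1.00 to about 1.66 over the common weeks and 1.00 to about 1.37 per person-week, rests on assumed detection probabilities and on p and q being the same in both arms. At the lower end there is no distortion beyond window length. The documents do not show that bias will occur or how large it would be. This is a worthwhile, inexpensive improvement to the harms record; it does not affect the primary analysis.

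**What to change.** Amend section 7.2.1 so that adverse events are also asked about in the same words and at the same weekly interval in both arms. Add two or three fixed items to the existing weekly online form from T0 to T4, covering, for example, any admission, any act of self-harm, any crisis or unplanned care, and any worsening that the patient links to the sessions. Keep spontaneous and observed reports as an additional source.

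Add to section 8 a descriptive report of events by arm in two forms: per person-week, so that the last 6 ImCT weeks are not dropped, and over the 22 weeks after randomisation common to both arms.

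Reconcile the new items with section 6.3.3, under which patients and therapists do not see assessment results until study end, by stating how the answers enter the adverse-event record.

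The cost is a short amendment, about one minute on a form that takes about 20, more minor events to log, and staff time to review the answers.
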